6.2.4. Non-study Medications

Non-study medications are coded using the World Health Organization (WHO) Drug Dictionary. The Prior, Concomitant, After (PCA) flag for non-study medications will be derived: prior non-study medications are defined as any non-study medications taken before the first dose of test article administration; concomitant non-study medications are defined as any medications taken during the treatment period (includes the 28 days after the last dose of the test article); after non-study medications are defined as any non-study medications taken during the follow-up period (more than 28 days after last dose).

6.2.5. Cross Intolerance

Patients who discontinued prior TKI therapy due to intolerance of imatinib, dasatinib, or nilotinib and who discontinue bosutinib due to the same AE or AE cluster will be classified as having cross intolerance.

6.2.6. Death

Death data will be collected during this study. Mandatory variables captured are date of death and cause of death. Deaths within 28 days of last dose and death due to study treatment toxicity are safety endpoints.

6.2.7. Adverse Events

A 3-tier approach will not be used to classify AEs since this study is a single-arm non-comparative study.

To ensure accuracy and consistency in data analysis and reporting, all adverse events must be classified using the Medical Dictionary for Regulatory Activities (MedDRA) before database lock (DBL). The severity of AEs will be assessed using the National Cancer Institute Common Terminology Criteria for Adverse Events (NCI CTCAE) version 4.0. The causal relationship between test article and an AE will be assessed by investigator's judgment.

6.2.8. Adverse Events of Special Interest

Adverse events including ALT, AST, thrombocytopenia (including MedDRA preferred term [PT] Platelet Count Decreased), neutropenia (including PT Neutrophil Count Decreased), leukopenia (including PT White Blood Cell Count Decreased), anemia (including PT Hemoglobin Decreased), diarrhea, nausea, vomiting, cardiac toxicity (definition to be determined before DBL), vascular toxicity (definition to be determined before DBL), and renal toxicity (definition to be determined before DBL) will be summarized. Additional AEs or AE clusters may be summarized if deemed appropriate. AE characteristics to be

summarized include maximum toxicity, time to first event, duration of any grade event, cumulative duration of grade 3/4 events, and successful rechallenge (those patients who were re-dosed and did not discontinue bosutinib due to this AE after having a dose delay).

6.3. Other Endpoints

6.3.1. Demographic, Medical History, and Baseline Characteristics

Demographic and baseline variables will include the following:

- Age ([the date of the signing of the informed consent form – the birth date]/365.25 in integer years), sex, race, height, and weight;
- Medical history;
- Cancer history (prior cancer history including CML and initial and current CML disease stage);
- Prior cancer therapies (interferon, imatinib, dasatinib, and nilotinib) and resistance/intolerance status for prior TKIs;
- Eastern Cooperative Oncology Group (ECOG) performance status.

6.3.2. PK Endpoints

There are no PK data being collected in this study.

6.3.3. PD Endpoints

There are no PD data being collected in this study.

6.3.4. Biomarker Endpoints

Blood and plasma samples will be collected for biobanking if specifically allowed by local EC/IRB. These samples will be retained for potential pharmacogenomic/biomarker analyses related to drug response, unless prohibited by local regulations or ethics committee decision. Formal analysis plans will be developed at a later date and will not be included in this SAP.

6.3.5. Outcomes Research Endpoints

Health Outcomes are measured using the FACT-Leu. The FACT-Leu will be administered at screening, weeks 13, 26, 39, 52, 78, 104, 130, 156, 182 and 208 (End of treatment) where the appropriate translations are available. The health outcomes assessment surveys are for the purpose of exploring the patient's own perceptions about his or her quality of life, and should be completed by the patient only prior to interaction with health care professionals at assigned study visits.

The FACT-Leu is a 44-item, self-reported, reliable and valid assessment of quality of life in patients with leukemia. The FACT-Leu consists of measures health related quality of life across 4 domains: Physical Well-being (7 items; score range, 0–28), Social/Family Well-being (7 items; score range, 0–28), Emotional Well-being (6 items; score range,

0–24), Functional Well-being (7 items; score range, 0–28 and a leukemia-specific subscale, which consists of 17 items (score range, 0–68) that assess patient concerns relating to leukemia. The total score (range, 0-176) can also be calculated. Patients are asked to rate on a scale from ‘0’ (“not at all”) to ‘4’ (“very much”), regarding how much each item (ie, pain, fatigue, etc.) was present in the last 7 days; higher scores reflect better quality of life. The minimally important difference (MID), defined as the smallest change in a PRO measure that is perceived by patients as beneficial, or that would result in a clinician considering a change in treatment for this instrument are defined as: 2-3 (PWB), N/A (SWB), 2 (EWB), 2-3 (FWB), 3-7 (FACT-G), 4-7 (LeuS-specific subscale) and 6-12 (FACT-Leu Total).

Each item in FACT-Leu is scored on a scale of 0, 1, 2, 3, and 4 for “not at all” to “very much”.

The score for each subscale is the sums of the scores of the items in that subscale. Because some of the items are positively stated and some negatively stated, the scores of the negatively stated items must be reversed so that the larger total scores will always indicate better health state. The FACT-Leu scoring guide identifies those items which must be reversed before being added to obtain subscale totals. The score for FACT-G is the sum of the subscale scores for PWB, SWB, EWB, and FWB. The score for FACT-Leu is the sum of the score for FACT-G plus the score for the subscale leukemia. FACT-Leukemia Trial Outcome Index (FACT-Leu TOI) will be calculated as sum of the PWB, FWB and LeuS sub-scale scores.

6.4. Covariates

Subgroup analyses by gender, age (<65, \geq 65), and race (Asian, Black, Other, White) will be explored as deemed appropriate. Additional supportive analyses may be explored if deemed appropriate.

7. HANDLING OF MISSING VALUES

In general, no imputation such as last observation carried forward (LOCF) will be used. For the time-to-event endpoints, such as time to response, DOR, time to transformation, PFS, and OS, the primary missing data handling method will be censoring as described in [Section 6.1](#).

In compliance with Pfizer standards for handling partial dates, if the month and year are present but day is missing, start date is set to 1st of month, and stop date is set to last day of month. If year is present but day and month are missing, start date is set to January 1st, and stop date is set to December 31st.

If there are missing items for the PRO endpoints, subscale scores can be prorated. This is done by multiplying the sum of subscale by the number of items in the subscale, then dividing by the number of items actually answered. This can be done on the scoring guide or by using the formula below:

Prorated subscale score = [Sum of item scores] x [N of items in subscale] \div [N of items answered]

When there are missing data, prorating by subscale in this way is acceptable as long as more than 50% of the items were answered (eg, a minimum of 4 of 7 items, 4 of 6 items, etc). The total score is then calculated as the sum of the unweighted subscale scores. The FACT scale is considered to be an acceptable indicator of patient quality of life as long as overall item response rate is greater than 80% (eg, at least 22 of 27 FACT-G items completed). This is not to be confused with individual subscale item response rate, which allows a subscale score to be prorated for missing items if greater than 50% of items are answered.

Handling of missing/incomplete patient central molecular data will be done by the following procedure: for post-baseline visits, assessments at a specific visit without a minimum number of ABL transcripts specified by the central laboratory will be not used for analysis.

Handling of missing/incomplete patient local cytogenetic data will be done by the following procedure: for baseline visits, only bone marrow information with ≥ 20 metaphases will be used, otherwise the baseline response will be set to missing. For post-baseline visits, bone marrow information with 20 to 99 metaphases will be used over FISH information with at least 200 nuclei at a specific visit. FISH will only be used to assess CCyR. No conventional bone marrow cytogenetic assessment will be derived when ≥ 100 cells are reported as analyzed for Philadelphia chromosome as this will be considered an error in data entry. If on-treatment molecular monitoring is performed in lieu of conventional cytogenetics or FISH, CCyR may be imputed on a specific date if a MMR is achieved on that date. The results of conventional cytogenetic testing, FISH with ≥ 200 nuclei or banding with ≥ 20 metaphases, will be used in preference to molecular testing, provided they are available and performed on the same date.

Handling of missing/mismatched patient hematologic efficacy data will be done using the following procedure: for each patient, the observations will be sorted by visit and the relative day to first dose.

First, for each observation, peripheral blood and/or bone marrow differentials should add up to 100%. Some sites may not record 0% to reflect uncounted cell types as instructed. Instead, the corresponding field may appear as missing or “ND” even though data collection procedures have been vigorously followed. Also, the differentials may not exactly add up to 100%. To correct this problem, each domain of the differentials will be summed together. If the total is between 98.5% and 101%, the missing values are assigned 0%. Otherwise, the observation is left as is and the record is also to be reported as a data issue.

Second, for the set of variables collected to derive peripheral blood or bone marrow differentials at each post-baseline visit up to week 13, if a given set are still incomplete, a non-missing set of lab variables obtained ± 3 days from the scheduled visit will be utilized to complete the derivation. For visits on or after week 13, a non-missing set of lab variables obtained ± 7 days of the visit will be utilized to complete that post-baseline assessment. The last non-missing peripheral blood or bone marrow differentials collected at week 1 day 1 or up to 30 days prior to week 1 day 1 will be used for baseline assessment. For example, if the bone marrow blast count was missing, the entire non-missing bone marrow assessment, not just the blast field, from another observation will be used. Some data handling rules for data combination are specified below.

- Data combination is needed only when the full dataset is not available on a single day at a given visit. The full dataset includes peripheral blood differential for chronic phase, and both bone marrow (when available) and peripheral blood differentials for advanced phase. The extramedullary assessment when absent should not preclude the derivation, and when present should be taken into account per response criteria rules.
- During the post-baseline data combination, the latest date will be used as the date of visit and the more conservative value will be taken if there is more than one measurement for a variable. For platelet counts, in case of multiple values, the lowest value will be taken. If any value falls above or below normal range, the out-of range value will be taken.

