Compared with imatinib, bosutinib was associated with higher incidences of grade 3-4 gastrointestinal toxicities, including diarrhea (12% vs. 1%), vomiting (3% vs. 0%) and abdominal pain (1% vs. <1%), although these adverse events were usually transient and manageable. Notably, diarrhea occurred mostly in the first 1-2 months of therapy and improved or subsided spontaneously over time. The rates of grade 3-4 non-hematologic toxicities were $\leq 1\%$ in both arms of the study. Grade 3-4 elevations of alanine aminotransferase (23% vs. 4%), aspartate aminotransferase (12% vs. 4%) or lipase (11% vs. 6%) were more frequent among patients treated with bosutinib compared to imatinib. Of those patients experiencing grade 3-4 elevations in transaminase levels in the bosutinib arm of this study, 91% were rechallenged. Of these patients, 80% did not experience subsequent elevations in transaminase levels that merited treatment discontinuation. Overall, 14% of patients were discontinued from bosutinib treatment due to unacceptable transaminase elevations. Grade 3-4 neutropenia, thrombocytopenia and anemia in the bosutinib and imatinib arms were 10% vs. 24%, 14% vs. 15% and 8% vs. 8%, respectively, indicating that bosutinib is at least as safe as imatinib regarding hematologic toxicity.

Ph+ Leukemia

Pooled safety data are reflected below (with a cutoff date of 15 November 2010). A total of 870 Ph+ leukemia patients across multiple, global Pfizer-sponsored clinical trials received at least 1 dose of single-agent bosutinib. These patients were either newly diagnosed Ph+ chronic phase CML, or were patients with resistant or intolerant Ph+ chronic, accelerated, or blast phase CML or Ph+ acute lymphoblastic leukemia (ALL). Of these patients, 248 are from the Phase 3 study in previously untreated CML patients, 570 and 52 are from two phase 1/2 studies in previously treated Ph+ leukemias. The median duration of therapy was 16.6 months (range: 0.03 to 30.4 months) in the Phase 3 study, 11 months (range: 0.03 to 55.1 months), and 5.5 months (range: 0.3 to 30.4 months), in the Phase 1/2 studies respectively.

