6.1. Screening

Screening can be accomplished over one or multiple visits over a 4-week period (30 days). Stage of disease is defined as the worst phase of CML experienced by the patient, regardless of disease status at the time of study entry. For example, a patient whose disease is in CP at study entry, but who had been previously diagnosed in AP, will be classified as AP CML. Refer to [Appendix 7](#) for specific criteria for CP, AP and BP phases of disease.

Prior cancer history, including CML and any other cancer will be collected. All treatments received by the patient for CML (CP, AP, and BP), including dates of administration, dose(s), best response and tolerability (including specific intolerance(s) to each therapy) will be collected from the time of original diagnosis of CML. Any additionally diagnosed malignancies will also be recorded at screening.

All relevant medical history and treatment received by the patient within 30 days before administration of bosutinib will be recorded on the patient's CRF, including the name of the procedure or drug and other related information.

The following procedures should be conducted as part of the baseline screening:

- Signature of informed consent document (ICD);
- Review of patient's eligibility (i.e., protocol inclusion/exclusion criteria);
- Cytogenetic confirmation of Ph+ chromosome (or BCR-ABL1+ if Ph-) CML diagnosis and phase. Acceptable documentation includes results from primary CML diagnosis or results following discontinuation/ failure of prior CML therapy. Either traditional cytogenetics for the Ph+ chromosome or fluorescence in situ hybridization (FISH) for the BCR-ABL juxtaposition or PCR for BCR-ABL transcript quantification are acceptable for the diagnosis of CML;
- Medical history;

- Complete physical examination to include vital signs (sitting or supine blood pressure, heart rate, and height and weight);
- Smoking status at screening; (Note: the use of TKIs could lead to cumulative long-term cardiovascular disease therefore information of other risk cardiovascular factors like smoking status will be collected for this study);
- Extramedullary disease assessment (including assessment of liver, spleen and lymph nodes by physical examination as well as other potential sites of extramedullary involvement);
- ECOG performance status ([Appendix 8](#));
- Electrocardiogram (ECG);

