8.1.4. Time Period for Collecting AE/SAE Information

The time period for actively eliciting and collecting AEs and SAEs (“active collection period”) for each patient begins from the time the patient provides informed consent, which is obtained before the patient’s participation in the study (ie, before undergoing any study-related procedure and/or receiving investigational product), through and including a minimum of 28 calendar days after the last administration of the investigational product.

For patients who are screen failures, the active collection period ends when screen failure status is determined.

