6.2. Safety Endpoints

Treatment-emergent adverse events (TEAE) are defined as any event increasing in severity from baseline or any new event starting during bosutinib therapy or within 28 days of the last dose of study drug (using 28 day lag).

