8.2.4.8. Adverse Events

The number and percentage of AEs listed below will be summarized overall and by MedDRA SOC and PT. Sorting will be done alphabetically by SOC and then by decreasing frequency of PT. AEs may also be summarized by other levels if deemed appropriate (eg, Higher Level Group Term [HLGT]).

- TEAEs;
- AEs leading to treatment discontinuations;
- TEAEs leading to dose reductions;
- TEAEs leading to dose delays;
- TEAEs by maximum toxicity grade (grades 1 to 5);
- TEAEs of higher toxicity grades (grades 3 or 4);
- TEAEs related to test article;
- Serious adverse events (SAEs);
- COVID-19 related TEAEs;
- TEAEs before and after initial dose reduction to 400 mg, 300 mg, and 200 mg due to an AE.

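### Adverse events in the calendar month of first dose with no recorded day are dated to the 1st, usually before treatment, and so fall out of the TEAE tables

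*SAP*

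**What the plan says.** SAP Section 7 gives one general rule for partial dates, attributed to sponsor standards. For a missing day it reads: "if the month and year are present but day is missing, start date is set to 1st of month". For a missing day and month: "If year is present but day and month are missing, start date is set to January 1st". Stop dates go the other way, to the end of the month or year. The rule does not name adverse events, but neither document contains another rule for their dates. Neither document limits an imputed start date to the first-dose date or treats a partially dated event as treatment-emergent by default.

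SAP Section 6.2 has two ways for an event to be treatment-emergent. The first is worsening, worded as "any event increasing in severity from baseline". The second is a fresh onset inside the treatment window, worded as "any new event starting during bosutinib therapy or within 28 days of the last dose of study drug".

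Protocol Section 8.1.4 says that active collection of adverse events "begins from the time the patient provides informed consent", so the database legitimately holds events that start before dosing.

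SAP Section 6.2.3 limits some calculations to complete dates, but only the timing and duration of laboratory events of special interest. It does not govern TEAE status.

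**The concern.** TEAE status depends on which side of first dose the start date falls. If the day is missing and the event arose after dosing in the same calendar month as first dose, the 1st of that month lies before first dose unless dosing began on the 1st. A new event on drug is then recorded as pre-existing. Its own grade becomes the reference severity, so the worsening limb brings it back only if a higher grade is recorded later. Since events are collected from consent, a start date before dosing would not look like an error to data management.

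SAP Section 8.2.4.8 builds most of its adverse event tables on this flag: overall, by maximum grade, grade 3 or 4, related, leading to dose reduction or delay, and before and after dose reduction. Describing the safety profile is a stated secondary objective. A misclassification tied to the start of treatment would therefore bear on the picture of early tolerability.

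**Working it through.** The plan gives no figure on this point, so there is none to reproduce.

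**Inputs from the documents.** The two imputation rules (SAP Section 7), the TEAE definition (SAP Section 6.2) and collection from consent (Protocol Section 8.1.4).

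**Assumptions, not in the documents.** First dose is uniform over calendar days. True onset is uniform over the first W days on drug.

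**Example.** First dose 14 March, true onset 20 March, day missing: the imputed start is 1 March, 13 days before dosing, so the event is not new on treatment. With true onset 5 April, the imputed start is 1 April, and the event is kept.

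**Calendar month of first dose, 30-day month.** A patient dosed on day d has 31 − d possible on-treatment onset days left in that month.
- All such onsets: 30 + 29 + … + 1 = 465.
- Those imputed before first dose (d = 2 to 30): 29 + 28 + … + 1 = 435.
- Share of events: 435/465 = 93.5%.
- Share of patients exposed to the problem: 29/30 = 96.7%. This is higher because patients dosed on the 1st, who lose nothing, have the most days left in the month.

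**First W days on drug.** An onset in a later calendar month is imputed after first dose and kept. The number lost is therefore the sum over d = 2 to 30 of min(W, 31 − d), out of 30 × W. The last column repeats the count over 1,096 real first-dose dates (2015–2017).

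| W (days) | Lost / total, 30-day month | Share | Real calendar |
|---|---|---|---|
| 7 | 182/210 | 86.7% | 86.9% |
| 14 | 315/420 | 75.0% | 75.4% |
| 28 | 434/840 | 51.7% | 52.4% |
| 30 | 435/900 | 48.3% | 49.1% |
| 56 | 435/1680 | 25.9% | 26.3% |

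Over the real calendar, the event share within the month of first dose is 93.6%. For year-only dates, 95.8% of onsets in the first 30 days are imputed before first dose.

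**From conditional to absolute.** All these shares are of events that lack a day. The proportion of events lacking a day is not given. If it were 2% to 5% (an assumption), the loss among all events in the first 30 days would be 0.02 × 0.483 = 1.0% to 0.05 × 0.483 = 2.4%.

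**Other boundary.** Last dose 5 March: the 28-day window closes on 2 April. A true onset on 20 April with the day missing is imputed to 1 April and counted as a TEAE. Protocol Section 8.1.4 sets 28 days as a minimum collection period, so such a record can exist.

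**With the proposed rule.** Over the same 1,096 dates, none of the day-missing onsets in the first 30 days is lost.

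**The case against.** The best case against is that very few events are likely to be affected. Early dates should be among the best recorded: visits fall in Weeks 1, 2, 3, 4 and 8, and diary cards with a date column are reviewed at them (Protocol Section 6.2 and Appendix 6). A patient with a later, fully dated episode of the same term still counts in a patient-level incidence. The tables of SAEs and of events leading to discontinuation in SAP Section 8.2.4.8 are not worded as TEAE tables and may still show these events. Laboratory toxicity is summarised from graded values. The study is single-arm and descriptive, with no hypothesis or decision rule. The sponsor standard that Section 7 cites may also contain an exception for first dose.

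All of this stands as a limit on size. None of it corrects the written rule. The standard is not in the documents, and the SAP states the rule without an exception.

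Three stronger readings are tempting and are not supported:
- A reader might infer that the rule always undercounts TEAEs. It does at first dose, but at the end of the 28-day window it can add events.
- A reader might infer that half of all first-month events vanish. The half applies only to events with a missing day.
- A reader might infer that the rule falls exactly where this population's diarrhoea is concentrated. Protocol Section 1.2.2 does say that "diarrhea occurred mostly in the first 1-2 months of therapy and improved or subsided spontaneously over time", but of the first-line phase 3 study rather than pretreated patients, and over a period nearer the 56-day row (26%) than the 30-day row.

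**Conclusion.** The rule is wrong as written for events in the calendar month, or for year-only dates the calendar year, of first dose. A new on-treatment event with a missing day in that month is classed as pre-treatment for every patient not dosed on the 1st, which is about 94% of such events. It stays out of the TEAE tables unless a later rise in severity is recorded. Over the first 30 days on drug, about 48–49% of day-missing onsets are lost.

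These shares rest on uniform dose and onset days; onset concentrated in the first week would raise them towards 87%. The direction at this boundary is undercounting of early TEAEs. The absolute effect cannot be computed from the documents and is probably small. A reader might infer that the study's safety conclusions are unsound, but nothing in the documents supports that. This is a specification error that is certain in mechanism and cheap to remove.

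**What to change.** Add to SAP Section 7, for adverse events: where the known month and year of onset (or the year, if only that is known) are those of first dose, the start date is set to the first-dose date for TEAE classification, unless the recorded stop date or other recorded data show onset before first dose. In all other cases the existing rule applies. If the sponsor standard already has such an exception, state it in the SAP.

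The cost is one sentence and a small programming change. The drawback is that some true screening events in the month of first dose will be counted as TEAEs when nothing recorded shows that they began earlier. Screening may last up to 30 days, so this can happen, but it is the conservative direction for safety. Reporting the number of adverse events whose TEAE status rests on an imputed date would show how much the choice matters.
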